9.3 Sub-Study Analyses

9.3.1 Clinic Experience

Clinic experience will be compared across the two arms of the study. Each question will receive an ordinal score from worst to best response. For each question, the score across trial arms will be compared using an mixed effects ordinal logistic regression model with a random intercept for the

treating clinician. We will perform subgroup analyses based on patient characteristics as described above for the primary analysis.

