Questions 1-4 have ordinal responses with linked questions as described above. For these questions, we will classify concordance as “concordant” if the categories match, “neither concordant or discordant” if the response categories differ by 1, and “discordant” if the response categories differ by >1. For question 5, we will classify as concordant or discordant. We will compare concordance between arms for each of these questions using mixed effects ordinal logistic regression with random intercepts for the treating clinician.

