Appendix B: Clinic Experience Survey

This survey is to evaluate your experience at your recent cardiology clinic visit. Using the 5-item scale below each question, please indicate how much you agree with the following statements by **marking the answer that best applies** to you :

1.) My clinician **listened to me** carefully:

 Completely agree	 Somewhat agree	 Neither agree nor disagree	 Somewhat disagree	 Completely disagree
--	--------------------------------------	--	---	---

2.) My clinician **understood symptoms** related to my heart:

 Completely agree	 Somewhat agree	 Neither agree nor disagree	 Somewhat disagree	 Completely disagree
--	--------------------------------------	--	---	---

3.) My clinician **showed respect** for what I had to say:

 Completely agree	 Somewhat agree	 Neither agree nor disagree	 Somewhat disagree	 Completely disagree
--	--------------------------------------	--	---	---

4.) My clinician and I **agreed on how I was doing overall**:

 Completely agree	 Somewhat agree	 Neither agree nor disagree	 Somewhat disagree	 Completely disagree
--	--------------------------------------	--	---	---

5.) My clinician **spent enough time** with me:

 Completely agree	 Somewhat agree	 Neither agree nor disagree	 Somewhat disagree	 Completely disagree
--	--------------------------------------	--	---	---

6.) My clinician explained things in a way that was easy to understand:

 Completely agree	 Somewhat agree	 Neither agree nor disagree	 Somewhat disagree	 Completely disagree
--	--------------------------------------	--	---	---

7.) I understand the **importance of taking the treatments** recommended by my clinician:

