 Completely agree	 Somewhat agree	 Neither agree nor disagree	 Somewhat disagree	 Completely disagree
--	--------------------------------------	--	---	---

8.) My goals regarding treatment and those of my clinician are aligned:

 Completely agree	 Somewhat agree	 Neither agree nor disagree	 Somewhat disagree	 Completely disagree
--	--------------------------------------	--	---	---

9.) What has the biggest impact on your quality of life?

 Heart Failure	 Other Cardiovascular Problems	 Other Medical Problems	 Heart Failure and Other Medical Problems	 Non-medical Reasons	 None of the Above
			Equally		

10.) In terms of your overall quality of life, how do you expect your heart failure health status to change over the following year:

 Significant Improvement	 Mild Improvement	 Remain Stable	 Mild Worsening	 Significant Worsening
---	--	-------------------------------------	--------------------------------------	---

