Appendix C: Clinician Perception of Health Status Survey

You saw _____ in clinic today. We have five questions regarding your perception of their heart failure health status (please circle all answers).

1.) What is their current New York Heart Association functional class?

NYHA Class I NYHA Class II NYHA Class III NYHA Class IV

2.) How much does heart failure impact their overall quality of life?

None Mildly Moderately Severely

3.) How frequently did they have the following symptoms in the last two weeks?

Edema	 None	 Once	 More than once, but not daily	 Daily	 I Don't Know
Orthopnea	 None	 Once	 More than once, but not daily	 Nightly	 I Don't Know
Fatigue	 None or once	 More than once, less than daily	 Daily	 Frequently each day	 I Don't Know
Shortness of breath	 None or once	 More than once, less than daily	 Daily	 Frequently each day	 I Don't Know

4.) In terms of their overall quality of life, how do you expect their heart failure health status to change over the following year:

Significant Improvement Mild Improvement Remain Stable Mild Worsening Significant Worsening

5.) What has the biggest impact on your patient's quality of life?

Heart Failure Other Cardiovascular Problems Other Medical Problems Heart Failure and Other Medical Problems Equally Non-medical Reasons None of the Above

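### Section 9.3.1 applies a worst-to-best ordinal analysis to every clinic experience question, but Question 9 has six unordered answers, so its arm odds ratio would depend on an arbitrary category order

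*Combined protocol and SAP*

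**What the plan says.** Section 9.3.1 sets one rule for the whole Clinic Experience Survey: "Each question will receive an ordinal score from worst to best response". It then names the model, in which the intercept varies by clinician: "For each question, the score across trial arms will be compared using an mixed effects ordinal logistic regression model with a random intercept for the". No question is exempted and no category order is listed. The same section adds subgroup analyses by patient characteristics.

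Appendix B has ten questions. Its introduction describes agreement items: "Using the 5-item scale below each question, please indicate how much you agree with the following statements by" marking an answer. Questions 1 to 8 fit that description. Question 9 asks "What has the biggest impact on your quality of life". Its six options are the ones printed again for clinician Question 5 in Appendix C: "Heart Failure Other Cardiovascular Problems Other Medical Problems Heart Failure and Other Medical Problems Equally Non-medical Reasons None of the Above". Question 10 asks "how do you expect your heart failure health status to change over the following year", with five answers running from significant improvement to significant worsening.

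Section 9.3.2 pairs clinician Question 4 with patient Question 10, and clinician Question 5 with patient Question 9. It describes clinician Questions 1 to 4 as ordinal and grades their agreement by the distance between categories. The fifth is handled differently: "For question 5, we will classify as concordant or discordant".

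**The concern.** An ordinal logistic model needs categories whose order means something. The Question 9 options name what most affects the patient's quality of life. None is a better or worse clinic experience than another, and the final catch-all option has no natural place on any scale. To carry out 9.3.1 as written, the analyst must invent an order, possibly after seeing the data. The direction of the arm effect, its size and its significance would then rest partly on that choice, and the same would hold in each subgroup. What is at stake is the interpretability of one reported comparison under patient experience, which the protocol lists among its secondary objectives (summary) and additional aims (section 4).

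**Working it through.** The plan gives no power, alpha or expected distribution for this analysis, so there is no figure of its own to reproduce. The check compares the texts and then illustrates the consequence.

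**Step 1: texts side by side.**

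| Patient item | Answers | Rule in 9.3.1 | Handling of the pair in 9.3.2 |
|---|---|---|---|
| Questions 1–8 | five ordered levels of agreement | ordinal | not used |
| Question 9 | six unordered causes | ordinal | match or no match |
| Question 10 | five ordered levels of expected change | ordinal | ordinal, by category distance |

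Only the Question 9 row conflicts: the same six options are ordinal in 9.3.1 and not ordinal in 9.3.2.

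**Step 2: illustration of order dependence.** The sub-study has about 600 patients (section 6.6), so about 300 per arm at 1:1 if all respond. The counts below are assumed; the documents give none. They follow the printed order of the options.

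- Usual care: 105/30/45/60/30/30 (sum 300).
- KCCQ arm: 81/30/45/84/30/30 (sum 300).

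The only difference is 24 patients (24/300 = 8 percentage points) who move from the first option, heart failure, to the fourth, heart failure and other medical problems equally.

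The model is logit P(Y ≤ k) = α_k − β × arm, fitted by maximum likelihood with a likelihood-ratio test and without the clinician random intercept. It was fitted under each of the 6! = 720 orders of the options:

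- Printed order: odds ratio 1.30, p=0.067.
- Fourth option moved to the first position, the others left as printed: odds ratio 0.87, p=0.34.
- All orders: odds ratio from 0.69 to 1.44; p<0.05 in 144 of 720 orders (20%).

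Reversing any order inverts its odds ratio, so the 720 orders form 360 mirror pairs, and a range that is symmetric around 1 on the log scale is automatic. The informative result is that the p-value also changes with the order.

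**Step 3: a test that ignores order.** In the Pearson chi-square on the 2 × 6 table, only the first and fourth options contribute. For the first, the expected count is (105 + 81)/2 = 93 per arm, giving 2 × 12²/93 = 3.10. For the fourth, it is (60 + 84)/2 = 72 per arm, giving 2 × 12²/72 = 4.00. The sum is 7.10 on (2 − 1)(6 − 1) = 5 df, p=0.21, whatever the order.

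**Step 4: sensitivity to the assumed counts.** A second assumed set, 90/30/60/60/30/30 against 75/30/75/75/20/25, gives an odds ratio of 1.05 (p=0.72) in the printed order, a range of 0.69 to 1.45, p<0.05 in 17% of orders, and chi-square 7.15 on 5 df, p=0.21. The individual numbers move with the inputs; the dependence on order remains.

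**The case against.** The best defence is that the sentence in 9.3.1 was meant for the agreement items and worded too broadly. The survey introduction speaks only of agreement on a five-level scale, and 9.3.2 gives Question 9 a use of its own and keeps its clinician pair out of the ordinal group. The authors evidently know that this response set is not ordinal, and a careful analyst would be unlikely to rank it. That is plausible as a reading of intent. The written rule still covers each question without exception, so a sensible analysis would have to depart from the plan.

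The illustration rests on invented counts, full response and no clinician intercept. That stands, and the figures support nothing beyond the mechanism.

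A reader might infer that Question 10 is equally wrong, because it asks about the coming year while the survey's stated purpose is "This survey is to evaluate your experience at your recent cardiology clinic visit". The documents do not support that. Question 10 is ordered, 9.3.2 treats its clinician pair as ordinal, and reversing its scale only inverts the odds ratio and leaves the p-value unchanged. Section 9.3.1 works question by question with no composite score, so the result can be reported as what it is. That it is best labelled as expected change in health status is a remark, not an error.

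A reader might also infer that the patient experience results as a whole are unsound. They are not: Questions 1 to 8 fit the rule, and no combined score carries Question 9 into them.

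**Conclusion.** The point holds for Question 9 and is minor. It rests on the text alone: 9.3.1 prescribes an ordinal analysis for an item with no order, and 9.3.2 treats the same six options as non-ordinal. This is a rule that is wrong as written for that item, not merely missing detail. The likely size of a distorted Question 9 result cannot be derived from the documents, because no response distribution is given. The effect is confined to one of ten items in a sub-study outcome. The primary endpoint, the listed secondary endpoints, the sample size and the data collection are not affected.

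**What to change.** In 9.3.1, exempt Question 9 from the worst-to-best scoring and the ordinal model. Then state one of two options:

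- Compare it between arms as a nominal outcome, using a multinomial model that keeps the treating-clinician effect. A plain chi-square test would drop that effect, which 9.3.1 specifies and by which randomization is stratified (section 6.3).
- Use it only in the concordance analysis of 9.3.2, where its handling is already suitable.

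Question 10 may keep the ordinal model; it would help to report it under its own wording.

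The cost is about one sentence and no new data. The downside of the nominal comparison is a test on five degrees of freedom with no single odds ratio to summarize it.

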9.3.2 Concordance Between Clinician and Patient Perception of Health Status

We will compare the concordance of health status assessment between patients and their treating clinician across the two arms. First, we will evaluate the proportion of explained variation of KCCQ-OSS via the clinician's NYHA score in each arm using linear regression.

Second, we will define concordance by linking the ordinal responses in the clinician survey to ordinal responses in the KCCQ-12 or the patient experience survey.

For question 1 of the clinician survey (NYHA Class), we will approximate patient estimation of NYHA category using their KCCQ-OSS score: KCCQ-OSS ≥ 80 – NYHA Class I, ≥ 60 to < 80 – NYHA Class II, ≥ 30 to < 60 – NYHA Class III, and < 30 – NYHA Class IV.

Question 2 of the clinician survey (quality of life) will be linked to the quality of life domain score. We will classify the response "none" as equivalent to a domain score > 80 , "mildly" as a score of ≥ 60 to < 80 , "moderately" as a score of ≥ 30 to < 60 and < 30 as "severely."

Question 3 of the clinician survey evaluates symptom frequency of edema, dyspnea, orthopnea, and fatigue on a 4-point ordinal scale with a 5th option of "I don't know." The following is the mapping between the KCCQ-12 responses and the clinician survey:

Edema	KCCQ	Never over past 2 weeks	Less than once per week	1-2 times per week	3 or more times per week but not every day	Every morning		
	Clinician Perception	None	Once	More than once, but not daily	More than once, but not daily	Daily		
Fatigue	KCCQ	Never over past 2 weeks	Less than once per week	1-2 times per week	3 or more times per week but not every day	At least once per day	Several times per day	All the time
	Clinician Perception	None	Once	More than once, but not daily	More than once, but not daily	Daily	Daily	Daily
Shortness of breath	KCCQ	Never over past 2 weeks	Less than once per week	1-2 times per week	3 or more times per week but not every day	At least once per day	Several times per day	All the time
	Clinician Perception	None	Once	More than once, but not daily	More than once, but not daily	Daily	Daily	Daily
Orthopnea	KCCQ	Never over past 2 weeks	Less than once per week	1-2 times per week	3 or more times per week but	Every night		

				not every day	
Clinician Perception	None	Once	More than once, but not daily	More than once, but not daily	Daily

Questions 4 and 5 in the clinician survey will be mapped directly to questions 10 and 9 in the patient experience surveys.

Questions 1-4 have ordinal responses with linked questions as described above. For these questions, we will classify concordance as “concordant” if the categories match, “neither concordant or discordant” if the response categories differ by 1, and “discordant” if the response categories differ by >1. For question 5, we will classify as concordant or discordant. We will compare concordance between arms for each of these questions using mixed effects ordinal logistic regression with random intercepts for the treating clinician.

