Secondary Endpoints	
Treatment patterns at 12 months:
 
 • Rates of guideline-directed therapy use • Dose of guideline-directed medical therapy • Advanced heart failure therapy evaluation • Cardiovascular testing 
Healthcare resource use at 12 months:
 
 • Heart failure clinic visits (in-person and televisits) • Heart failure telephone encounters (other than visits) • Emergency department visits • Hospitalizations (heart failure and non-heart failure)
Other Outcomes of Interest in Sub-Study	
 • Clinician perception of health status • Patient experience
Assessment Schedule	
 • Baseline KCCQ-12 at time of first clinic visit • Repeat KCCQ-12 within 12-15 months post-randomization 
Sub-study:
 
 • Patient experience survey • Clinician evaluation of patient health status
Study Duration	Patients will be enrolled for 12 months. Expected follow-up will be 12-15 months post-randomization. Patients will be followed until their first clinic visit after one year. Patients without a follow-up visit within 15 months, will be contacted for final outcome ascertainment at that time.
Statistical Considerations	A sample size of 1,200 randomized participants has 95% power to detect a mean difference in KCCQ-12 of 5 between arms (72 in KCCQ arm versus 67 in usual care; SD ~24) and an 80% power to detect a mean difference in KCCQ-12 of 4 without covariate adjustment.

TABLE OF CONTENTS

1. LIST OF ABBREVIATIONS AND DEFINITONS	5
2. BACKGROUND AND RATIONALE	6
3. HYPOTHESIS	8
4. STUDY OBJECTIVES	9
5. STUDY DESIGN	10
6. STUDY PROCEDURES	13
7. TREATMENT ARMS	17
8. STUDY ASSESSMENT AND SCHEDULE	18
9. STATISTICAL CONSIDERATIONS AND ANALYSIS PLAN	19
10. DATA HANDLING AND RECORD KEEPING	23
11. DATA AND SAFETY	24
12. PROTOCOL AMENDMENTS	25
13. REFERENCES	26
14. APPENDICES	27

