8.2.3 Clinician Perception of Health Status

The clinician perception of health status survey will be completed by the treating clinician for each patient in the sub-study following their first heart failure clinic visit post-randomization. The survey will be distributed on paper but also be available online. The clinician perception of health status survey is shown in Appendix C.

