Appendix A: Kansas City Cardiomyopathy Questionnaire-12

Kansas City Cardiomyopathy Questionnaire (KCCQ-12)

The following questions refer to your **heart failure** and how it may affect your life. Please read and complete the following questions. There are no right or wrong answers. Please mark the answer that best applies to you.

1. **Heart failure** affects different people in different ways. Some feel shortness of breath while others feel fatigue. Please indicate how much you are limited by **heart failure** (shortness of breath or fatigue) in your ability to do the following activities over the past 2 weeks.

Activity	Extremely Limited	Quite a bit Limited	Moderately Limited	Slightly Limited	Not at all Limited	Limited for other reasons or did not do the activity
a. Showering/bathing						
b. Walking 1 block on level ground						
c. Hurrying or jogging (as if to catch a bus)						

2. Over the past 2 weeks, how many times did you have **swelling** in your feet, ankles or legs when you woke up in the morning?

Every morning	3 or more times per week but not every day	1-2 times per week	Less than once a week	Never over the past 2 weeks
				

3. Over the past 2 weeks, on average, how many times has **fatigue** limited your ability to do what you wanted?

All of the time	Several times per day	At least once a day	3 or more times per week but not every day	1-2 times per week	Less than once a week	Never over the past 2 weeks
						

4. Over the past 2 weeks, on average, how many times has **shortness of breath** limited your ability to do what you wanted?

All of the time	Several times per day	At least once a day	3 or more times per week but not every day	1-2 times per week	Less than once a week	Never over the past 2 weeks
						

5. Over the past 2 weeks, on average, how many times have you been forced to sleep sitting up in a chair or with at least 3 pillows to prop you up because of **shortness of breath**?

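### The section 9.3.2 crosswalk for fatigue and shortness of breath uses answer categories the clinician form does not offer, so the concordance rule cannot be applied as written to these two items

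*Combined protocol and SAP*

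**What the plan says.** Section 9.3.2 describes one scale for all four symptoms: "Question 3 of the clinician survey evaluates symptom frequency of edema, dyspnea, orthopnea, and fatigue on a 4-point ordinal scale", with a fifth option for not knowing. It then introduces a table with the words "The following is the mapping between the KCCQ-12 responses and the clinician survey". In that table fatigue and shortness of breath share one set of target categories: *None*, *Once*, *More than once, but not daily* (used for two KCCQ-12 answers) and *Daily* (used for three). Edema and orthopnea have the same four categories.

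The same section then classifies each pair. Matching categories are concordant, categories one apart are neither concordant nor discordant, and a pair is discordant "if the response categories differ by >1". The rule covers clinician questions 1 to 4, so it includes every symptom in question 3.

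Appendix C prints different choices for fatigue and shortness of breath: *None or once*, *More than once, less than daily*, *Daily* and "Frequently each day". Edema has the table's labels exactly. Orthopnea differs only in having *Nightly* where the table has *Daily*.

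**The concern.** A distance rule needs both answers on one ordered scale. For these two symptoms each side has four levels, but not the same four. The clinician cannot tick *None* and *Once* separately. No patient answer is sent to the form's top option, although KCCQ-12 items 3 and 4 in Appendix A offer "Several times per day" and an all-of-the-time answer, which are its natural counterparts.

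The analyst must therefore supply a recode, and the classification depends on which one. Under some codings answers that agree are scored as neither or cannot be scored. Under others, answers that do not agree are scored as concordant. That blurs the concordance measure and can alter the between-arm comparison. If the coding is chosen after the data are seen, the results for these items are also open to selection.

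**Working it through.** The plan gives no figure to reproduce here. The check sets the two scales side by side and then enumerates the answer pairs.

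**Inputs.** Seven KCCQ-12 answers (Appendix A, items 3 and 4), the category each receives in the section 9.3.2 table, and the four Appendix C options, leaving out *I Don't Know*. *But not daily* and *less than daily* are treated as the same label.

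| KCCQ-12 answer | 9.3.2 category (rank) | Nearest Appendix C option (rank) | Rank difference |
|---|---|---|---|
| Never | None (1) | None or once (1) | 0 |
| Under once a week | Once (2) | None or once (1) | 1 |
| 1-2 a week | More than once (3) | More than once (2) | 1 |
| 3 or more a week | More than once (3) | More than once (2) | 1 |
| At least once a day | Daily (4) | Daily (3) | 1 |
| Several a day | Daily (4) | Frequently each day (4) | 0 |
| All the time | Daily (4) | Frequently each day (4) | 0 |

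**Agreeing answers, out of 7, that are mis-scored or cannot be scored**

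- By position: 4, the rows with difference 1.
- By label: 4. The agreeing clinician option is absent from the table for the first two and last two rows.
- *None* and *Once* merged, nothing else changed: the plan ranks become 1, 1, 2, 2, 3, 3, 3 against 1, 1, 2, 2, 3, 4, 4, so 2.
- Both sides collapsed to three levels: 0. The plan does not state this collapse.

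Placing *at least once a day* with *Frequently each day* is also arguable. On that reading the four counts are 3, 5, 3 and 0.

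**All pairs.** 7 patient answers x 4 clinician options = 28 pairs per item, classed by absolute rank difference (0, 1, more than 1):

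| Coding | Concordant | Neither | Discordant | Pairs classed differently from the form's own options |
|---|---|---|---|---|
| Form's own four options | 7 | 10 | 11 | reference |
| By position | 7 | 10 | 11 | 14 |
| None and Once merged | 7 | 12 | 9 | 6 |
| Three-level collapse | 10 | 11 | 7 | 7 |

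The 14 by position are 4 concordant to neither, 4 neither to concordant, 3 neither to discordant and 3 discordant to neither. For example, a patient answering 1-2 times a week with a clinician ticking *Daily* is 3 against 3, concordant. On the form's own scale it is 2 against 3, neither. The 6 are 2 concordant to neither, 2 neither to concordant and 2 discordant to neither. If *at least once a day* is set to the top option in the reference, 14 becomes 11 and 6 becomes 9.

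By label, 2 of the 4 clinician options are missing from the table, so 2 x 7 = 14 pairs cannot be scored. Counting a missing category on either side gives 2 x 4 + 5 x 2 = 18. All four codings in the table agree on only 8 of 28 pairs.

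**The case against.** The strongest reply is that the intent is clear. The table works by label and sends every daily-or-more answer to *Daily*, so a sensible analyst would merge *None* with *Once* and fold *Frequently each day* into *Daily*. No agreeing answer is then mis-scored. Coding by position contradicts the labels, so 14 of 28 is a worst case. This stands as a point about plausibility, but the plan does not state the collapse. It also differs from the form-based crosswalk on 7 of 28 pairs (4 discordant become neither, 3 neither become concordant), so one coding has to be chosen in advance.

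Second, any fixed coding applies equally to both arms. If the joint distribution of patient and clinician answers is the same in each arm, miscoding alone creates no difference. That is right, and the main harms are a blurred measure and a post hoc choice. Equal distributions cannot be assumed, however. Section 6.4.3 has the KCCQ-12 printed for the clinician in the intervention arm only. A clinician who reads that fatigue occurs several times a day and ticks the top option would be scored as neither if only *None* and *Once* were merged. This shows a possible mechanism; it does not establish a direction.

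Third, the scope is small. The Clinical Trial Summary lists clinician perception under "Other Outcomes of Interest in Sub-Study" and section 4 places it among additional aims, although the Summary's objectives count concordance as secondary. That limits the weight of the point without removing it.

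**Conclusion.** The concern holds. For fatigue and shortness of breath the table does not fit the form, and no recode is given. This affects 2 of the 8 item-level comparisons (questions 1 and 2, four symptoms in question 3, questions 4 and 5) in a sub-study of about 600 patients. The primary endpoint, the regression of KCCQ-OSS on NYHA class and the other six items are unaffected. It should be fixed before the concordance analysis.

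The size depends on the coding chosen: 0 to 4 of 7 agreeing answers are mis-scored or unscorable (0 to 5 on the alternative reading of *at least once a day*). The pair counts are unweighted combinations, not expected patient frequencies, which the documents do not give. Agreement here refers to the frequency wording only. The KCCQ-12 asks how often the symptom "limited your ability to do what you wanted", whereas the clinician form asks how often it occurred. The conclusion also assumes that Appendix C is the form actually used.

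**What to change.** First confirm that the Appendix C wording was used in both modes. Section 8.2.3 says: "The survey will be distributed on paper but also be available online". If the fielded form differed, the appendix is what needs correcting.

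Then replace the two table rows with one crosswalk to the form's own options:

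- never, and less than once a week: *None or once* (1)
- 1-2 times, and 3 or more times, a week: *More than once, less than daily* (2)
- at least once a day: *Daily* (3)
- several times a day, and all the time: *Frequently each day* (4)

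The alternative is to collapse both sides to three levels, with *Daily* and *Frequently each day* combined. That loses the top distinction but avoids the judgement about *at least once a day*. The two are not interchangeable, so name one as the analysis before it is run.

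State the numeric codes to which the distance rule applies, and state that *I Don't Know* is outside the ordinal comparison. Changing *Daily* to *Nightly* in the orthopnea row is cosmetic.

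The cost is an edit to two rows of one table and two added sentences. No new data are needed if the fielded wording is as printed.
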